**REVISION HISTORY**

Revision #	Version Date	Summary of Changes	Consent Change?
1	3.1.2022	Adding a telephone MoCA as an additional screening tool	No

## 1.0 Study Summary

Study Title	Home-based Transcranial Direct Current Stimulation for Pain Management in Persons with Alzheimer's Disease and Related Dementias
Study Design	Double-blind, randomized, sham-controlled, parallel group (1:1 for two groups) design.
Primary Objective	The purpose of this project is to assess the effect of the self-administered transcranial direct current stimulation (tDCS) in 40 older adults with ADRD
Secondary Objective(s)	The specific aims are the following: evaluate the preliminary effects of home-based M1-SO applied tDCS on clinical pain in persons with early-stage ADRD (specific aim 1); evaluate the preliminary effects of home-based M1-SO applied tDCS on pain related cortical response in persons with early-stage ADRD (specific aim 2); and evaluate the feasibility and acceptability of home-based M1-SO–applied tDCS for pain management in persons with early stage ADRD (specific aim 3).
Research Intervention(s)/Investigational Agent(s)	tDCS
IND/IDE #	N/A
Study Population	Older adults with early-stage Alzheimer's Disease and Related Dementia (ADRD)
Sample Size	40
Study Duration for individual participants	3 months, including follow-up phone interviews
Study Specific Abbreviations/Definitions	tDCS, transcranial direct current stimulation; ADRD, Alzheimer's Disease and Related Dementia, SMC, Safety Monitoring Committee

## **2.0 Objectives**

The purpose of this project is to assess the feasibility, acceptability, and preliminary effects of this novel nonpharmacological treatment option in persons with ADRD. The specific aims are the following: evaluate the preliminary effects of home-based M1-SO applied tDCS on clinical pain in persons with early-stage ADRD (specific aim 1); evaluate the preliminary effects of home-based M1-SO applied tDCS on pain-related cortical response in persons with early-stage ADRD (specific aim 2); and evaluate the feasibility and acceptability of home-based M1-SO applied tDCS for pain management in persons with early-stage ADRD (specific aim 3). Outcome measures include clinical pain, pain-related cortical response using functional near-infrared spectroscopy, and participant experience and side effects using questionnaire.

## **3.0 Background\***

The World Health Organization has highlighted dementia care as one of its highest priorities. Alzheimer's disease and Related Dementias (ADRD) is characterized by progressive and global deterioration in cognitive functions, and more than 5.5 million people in the United States have ADRD. Persons with ADRD are often elderly and have many age-related sources of pain (e.g., radiculopathy and arthritis), with approximately 60% reporting chronic pain. Aside from behavioral and psychological symptoms of dementia (BPSD), pain is the most cited cause for decreased quality of life in persons with ADRD. Moreover, our group and others showed that pain in ADRD is associated with neuropsychiatric symptoms and a decline in cognitive functioning. Primary treatment options for pain management comprise mainly the prescription of analgesic medications; however, existing pharmacological approaches often produce significant adverse events (e.g., constipation, confusion, behavioral disorders, psychomotor retardation, and falls), and the treatment benefits may decrease over time (e.g., drug tolerance development). Furthermore, many studies suggest that alterations in pain related brain mechanisms may contribute to chronic pain. Indeed, neuroimaging studies have revealed increased pain-related brain activation in people with chronic pain, and alterations in pain related brain mechanisms have been associated with chronic pain and disability in older adults. Therefore, there is growing interest in nonpharmacological interventions targeting pain-related brain function in this population. Noninvasive brain stimulation, such as transcranial direct current stimulation (tDCS), has received significant attention as treatment of pain in chronic conditions owing to its neuromodulatory effects in the central nervous system. tDCS involves the application of low-amplitude direct electric current to the head in a noninvasive and painless manner, which modulates the resting membrane potentials of neurons, altering the excitability of the targeted cortical area. Hundreds of clinical trials have demonstrated that tDCS is safe and well tolerated within the established current intensities and durations. For pain treatment, stimulation is typically delivered multiple times with the anode electrode placed over the primary motor cortex of the left hemisphere and with the cathode electrode placed over the contralateral supraorbital region. A panel of experts of the International Federation of Clinical Neurophysiology published evidence-based guidelines in which they recommended 20-minute tDCS using 2 mA electrical current intensity for possible efficacy among populations with chronic pain.

Therefore, we will examine the effect of tDCS in persons with ADRD. Our hypothesis is that remotely supervised tDCS at home will decrease clinical pain.

#### **4.0 Study Endpoints\***

The study endpoint is 3 months, including monthly follow-up telephone assessments for 3 months after the completion of intervention.

#### **5.0 Study Intervention/Investigational Agent**

tDCS with a constant current intensity of 2 mA will be applied for 20 minutes per session daily for 5 days via the Soterix 1x1 tDCS mini-CT Stimulator device (Soterix Medical Inc., NY; 6.5 inches long, 3 inches wide, 0.7 inches thick) with headgear and 5x7 cm saline-soaked surface sponge electrodes. The FDA has ruled that the aforementioned tDCS stimulator is a “non-significant risk” device, a requirement for Investigational Device Exceptions. The sponge electrodes snap into the custom headgear, which is secured to the participant’s head for simple and fail-safe electrode preparation. This single-position headgear with clearly labeled sponge markers eliminates room for user error and helps conserve the placement of the montage. Participants can only administer a stimulation session via the Soterix 1x1 tDCS mini-CT Stimulator device after being provided a single-use unlock code by the research staff once proper contact quality is achieved (only the on/off button will be adjustable by the study participants; they will not be able to adjust the device settings). After the participant enters the unlock code, the screen on the device will show a timer that counts down the minutes until the end of the session. At 20 minutes, the device will turn off automatically, and study staff will instruct the participant to remove the headset and discard the sponges and to safely store all materials for the next session. For sham stimulation, the electrodes will be placed in the same positions as for active stimulation, but the stimulator will only deliver 2 mA current for 30 seconds. This sham stimulation method has been shown to be reliable and indistinguishable from active treatment.

#### **6.0 Procedures Involved\***

Alzheimer’s disease and Related Dementias (ADRD) affects more than 5.5 million individuals in the United States. Approximately 60% of persons with ADRD experience chronic pain, and pain is the second most commonly cited reason for decreased quality of life in persons with ADRD. Our group and others showed pain in ADRD is associated with behavioral and psychological symptoms of dementia. The current standard of care comprises mainly the prescription of analgesic medications, which often produce significant adverse effects. Moreover, recent evidence suggests that alterations in pain-related brain mechanisms may contribute to chronic pain. Therefore, there is growing interest in nonpharmacological interventions targeting pain-related brain function in this population. One promising treatment is tDCS with the anode over the primary motor cortex and the cathode over the contralateral supraorbital area (M1-SO applied tDCS), as it can change brain activity in a noninvasive, painless, and safe way. We will investigate the effects of home-based, remotely supervised, M1-SO applied tDCS on clinical pain in 40 persons with early-stage ADRD using an experimenter- and participant-blinded,

randomized, sham-controlled, parallel group (1:1 for two groups) pilot clinical trial. The central hypothesis is that home-based, remotely supervised tDCS will decrease pain. This hypothesis will be tested by pursuing the following specific aims: evaluate the preliminary effects of home-based M1-SO applied tDCS on clinical pain in persons with early-stage ADRD (specific aim 1); evaluate the preliminary effects of home-based M1-SO applied tDCS on pain related cortical response in persons with early-stage ADRD (specific aim 2); and evaluate the feasibility and acceptability of home based M1-SO-applied tDCS for pain management in persons with early stage ADRD (specific aim 3). We will also obtain data, as an exploratory aim, to investigate whether tDCS reduces behavioral and psychological symptoms of dementia. The proposed study will directly investigate the effects of home-based, remotely supervised tDCS in 40 persons with ADRD using an experimenter- and participant-blinded, randomized, sham-controlled, parallel group (1:1 for two groups) pilot clinical trial. Caregivers will set up and administer home-based tDCS for persons with ADRD and must be present at each home-based session, and participants will be remotely supervised by trained research staff at each stimulation to ensure the use of proper technique. Primary outcome (clinical pain assessed by the MOBID-2) will be performed by the caregivers. Caregivers will be trained at the in-person baseline visit to use tDCS devices and to perform outcome measures. tDCS session will be not performed if the caregiver is not available, and it needs to be the same caregiver throughout the trial. The proposed research is significant because it is expected to provide valuable insight into an exciting new modality of nonpharmacological pain management that is easy, safe, and noninvasive with minimal side effects.

Participants will do remotely-supervised tDCS at their home or private room for 5 days under real time supervision by the research staff. Data will be collected by study staff across several points using equipment and resources available at [name] (PI's) laboratory at Florida State University (see Table below). The primary endpoint will be clinical pain (MOBID-2) collected after the final intervention session. Participants will visit Florida State University two times, and each visit will take approximately 2 hours.

Research subjects/caregivers will be called one day prior to their scheduled study visit and asked a series of COVID-19 related questions covering topics such as isolation and quarantine, vaccination status, symptoms, test results, and exposure. And then subjects will be notified about the FSU COVID-19 precautions. Consent materials will be modified to include a statement to the effect that no in-person activity may involve any individual (human research participants (human subjects) or study staff—vaccinated or unvaccinated) who (1) tests positive for COVID-19 or (2) has been in close contact with someone who has COVID-19, within at least the past 10 days of the positive COVID-19 test or close contact; that prospective subjects will be screened for this purpose; and that for any in-person research activity the use of masks is strongly recommended (and may be required in certain locations) as is a full COVID-19 vaccination.

Table 1. Timetable for Collection of Data

		Week 1	F1	F2	F3
--	--	--------	----	----	----

Stimulation Session	Baseline	1	2	3	4	5			
MMSE	X								
Medical History Questionnaire	X								
Clinical Pain (MOBID-2): primary outcome	X	X	X	X	X	X	X	X	X
Clinical Pain (NRS): secondary outcome	X	X	X	X	X	X	X	X	X
BPSD (CMAI, NPI): secondary outcome	X					X	X	X	X
Pain-related cortical response (fNIRS): secondary outcome	X					X			
tDCS experience questionnaire: secondary outcome						X			
Patient satisfaction (CSQ-8): secondary outcome						X			
Side effects questionnaire: secondary outcome		X	X	X	X	X			

Note: F, Weekly follow-up phone assessment after completion of tDCS treatment; MMSE, Mini-Mental Status Exam, MOBID, Mobilization-Observation-Behavior-Intensity-Dementia Pain Scale; BPSD, behavioral and psychological symptoms of dementia; CMAI, Cohen-Mansfield Agitation Inventory; fNIRS, functional near-infrared spectroscopy; CSQ, Client Satisfaction Questionnaire.

- MMSE. MMSE will be used to exclude people with severely diminished cognitive function (i.e., Mini-MentalStatus Exam score  $\leq 15$ ).
- Medical History Questionnaire. All participants will complete a thorough questionnaire to collect demographic and medical history details, including age, sex, height, weight, duration of knee OA, current and past treatments for knee OA, comorbid conditions, and current medications.
- Clinical pain will be measured to rate patients' pain via the Mobilization-Observation-Behavior Intensity-Dementia (MOBID-2) scale from 0 to 10, which will be primary outcome measure for data analysis purposes. The MOBID-2 is a well-validated measure with good ability to detect painchange in persons with ADRD. We also measure clinical pain by asking participants to rate their average pain over the past 24 hours via NRS from 0 (no pain) to 100 (worst pain imaginable), following Initiative on Methods, Measurement, and Pain Assessment in Clinical Trials recommendations for clinical trials involving chronic pain. NRS is appropriate for use among older adults with mild to moderate dementia.
- BPSD. NPI will be used to obtain information on behavioral and psychological symptoms of the patients. NPI comprises 12 items that are summed to yield an overall score of 0-144 (each item will be rated frequency X severity, totaling 0 – 12), with higher scores indicating greater symptoms. We also collect CMAI, which is comprised of 29 items that are summed to yield an overall score of 29-203 (each item will be rated 7-point scale of frequency). Trained research staff will conduct the NPI interview. In terms of training, two raters (one primary and one back-up) conduct mock administrations to each other. Same rater will conduct the assessment with the subjects for fidelity. PI will

- review NPI and CMAI and will not refer subjects for clinical review based on the result.
- A multichannel fNIRS imaging system (LIGHTNIRS, Shimadzu, Kyoto, Japan) will be used to determine changes in regional cerebral blood flow in response to thermal stimuli applied to the right forearm of participants. The illumination and detection optodes will be arranged in a geometrical layout that will cover the prefrontal and somatosensory cortex regions bilaterally, consistent with locations investigated in previous studies. For evoked pain scans, low-intensity thermal stimuli at the thermal pain threshold level will be applied for a few seconds during multiple scanning runs, followed by an approximately equivalent interval of no stimulation, which is commonly used in pain related neuroimaging studies since thermal hyperalgesia is an important component of chronic pain. A temperature-controlled pain generator (Medoc TSA-II Neurosensory Analyzer) will be used to produce thermal stimulation through a 16 mm  $\square$  16 mm thermode. We expect to observe reduced pain-evoked activation in the active tDCS group in the prefrontal and somatosensory cortices. To minimize the inconvenience to participants, we will deliver thermal stimuli that are below the individual's pain tolerance level and set the cutoff temperature at 50°C. These procedures will ensure maximum patient safety and comfort while allowing successful and reliable imaging of the pain-related cortical response.
- We will collect data on the tDCS experience via a questionnaire, adapted from Gillick et al. and Cha et al., at the conclusion of tDCS treatment on a 0 (strongly disagree) to 10 (strongly agree) scale: 1) It was easy to prepare the device and accessories; 2) The device was unnecessarily complex; 3) The device was easy to use; 4) I felt the video conferences with a technical person were helpful; 5) I would imagine that most people would learn to use this device quickly; 6) The device was cumbersome to use; 7) I felt confident using the device; 8) I needed to learn a lot of things before I could get going with this device; 9) The effectiveness of the treatment increased over the course of treatment; and 10) Overall, I felt that transcranial electrical stimulation treatment benefited me. Participants/caregivers will also be encouraged to elaborate on their answers in free form. In addition, we will measure participant satisfaction with treatment using the Client Satisfaction Questionnaire (CSQ-8). The CSQ-8 comprises eight items that are summed to yield an overall score of 8-32, with higher scores indicating greater satisfaction. Moreover, we will evaluate the presence and severity of possible side effects of treatment at the end of each session on a 0 (not at all) to 10 (highest degree) scale. The participants will be asked in an open-ended manner whether they experienced any side effects, and they will then be asked specifically about tingling, itching sensation, burning sensation, pain at the stimulation site, fatigue, nervousness, headache, difficulty concentrating, mood change, and changes in vision or visual perception. If any side effects are reported, the degree of relatedness to the intervention will be assessed on a 5-point scale. This approach has been used in our previous study and frequently in other studies.

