## **12.0 Local Number of Subjects**

The number of subjects who are expected to be enrolled and screened is 24, and the number of subjects needed to complete the research procedures (i.e., numbers of subjects excluding screen failures.) is 20. The total number of subjects to be accrued locally is 20, since we completed data collection for 20 subjects at the University of Texas Health Science Center at Houston before PI ([name]) moved to Florida State University.

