## **18.0 Provisions to Monitor the Data to Ensure the Safety of Subjects**

[name], the PI, will have the primary responsibility for monitoring study research staff, who will receive training on the study design, recruitment, and protocol prior to study initiation. The research staff will attend weekly meetings with the PI and monthly team meetings during data collection with the PI and co-investigators to discuss any study-related issues regarding recruitment and follow-up data collection. These meetings will be used to discuss experiences with the intervention participants, provide consultation, ascertain whether the research staff are following study protocols, evaluate and reinforce cultural competence, and identify any potential adverse events. [name], the study statistician, will coordinate data management and analysis.

The Safety Monitoring Committee (SMC), which was approved by NIH, will be responsible for overseeing activities related to implementing the clinical trial to ensure patient safety, conformance to the clinical protocol, overall performance of the trial components, and integrity of the data being collected. The SMC will meet prior to the start of enrollment and then annually to review study progress (e.g., recruitment, retention, and safety procedures) and participant safety concerns and as needed to adjudicate any adverse events. All meeting materials will be considered privileged by SMC members. The SMC will comprise 3 members with expertise in neuromodulation, statistics, and geriatric clinical research: [name], professor of psychiatry and behavioral sciences at Baylor College of Medicine; [name], associate professor and biostatistician at the UTHealth Cizik School of Nursing; and [name], Assistant Professor, Geriatric and Palliative Medicine, UTHealth McGovern Medical School. The SMC members are independent of the project. These members are appropriately qualified to review the scientific design and conduct of the study, to evaluate safety and risks to participants, to interpret data statistically, and to make recommendations concerning the continuation, modification, suspension, or termination of the study.

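### The protocol bars clinical referral on any NPI or CMAI result, with no exception for marked worsening: a low-priority safety wording to correct

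*Protocol*

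**What the plan says.** The rule is in Protocol section 6.0, in the item on behavioural and psychological symptoms. The principal investigator will "review NPI and CMAI and will not refer subjects for clinical review based on the result". A bullet break splits the sentence in the text but does not change its meaning. No threshold, exception or alternative action follows.

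Table 1 in the same section schedules NPI and CMAI at baseline, session 5, F1, F2 and F3. The row "Side effects questionnaire: secondary outcome" is marked at sessions 1 to 5 only. That questionnaire opens with a general question and then asks about listed symptoms, among them nervousness and mood change. Where something is reported, "the degree of relatedness to the intervention will be assessed on a 5-point scale".

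Section 18.0 sets out the adverse-event route. Weekly and monthly staff meetings serve, among other purposes, to "identify any potential adverse events". The Safety Monitoring Committee meets annually and "as needed to adjudicate any adverse events". Neither scale is named there, and the SAP does not mention them.

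**The concern.** This is a written rule, not a silence. Read literally, a participant with dementia could show a marked rise in agitation or neuropsychiatric symptoms, the principal investigator could see it, and the protocol would rule out referral on that finding. Whether the change is also assessed as an adverse event is left to judgement that the protocol neither describes nor prompts.

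Section 6.0 frames the exploratory aim as whether stimulation reduces these symptoms. The same scales can move the other way, and the plan assigns no action to that case. The Background (section 3.0) counts behavioural disorders among the adverse events of analgesic drugs, so the protocol does treat this kind of change as a harm when another pain treatment causes it.

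What is at stake is the care of individual participants, not the validity of the trial's inference.

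**Working it through.** The plan gives no figure on this point, so the check sets the texts side by side and counts occasions.

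**Step 1: what is scheduled when (Protocol section 6.0, Table 1).**

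| Time | NPI and CMAI | Side-effects questionnaire with relatedness rating | MOBID-2 and NRS pain |
|---|---|---|---|
| Baseline | yes | no | yes |
| Sessions 1 to 4 | no | yes | yes |
| Session 5 | yes | yes | yes |
| F1, F2, F3 | yes | no | yes |

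At session 5 a behavioural change can also surface through the side-effects questionnaire. At F1 to F3 it cannot. MOBID-2 continues and observes behaviour, but as a sign of pain. NPI and CMAI are then the only scheduled measures aimed at behavioural and psychological symptoms in general. The length of this window is unclear: section 4.0 calls the follow-up calls monthly, while the note to Table 1 calls them weekly.

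**Step 2: does any other text connect a worsening score to an action?**

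- Section 18.0: the route covers any adverse event, but someone must first regard the change as one. No score is mentioned.
- Section 6.0, side effects: the relatedness rating applies to reported side effects, not to score changes.
- Section 20.0: a study physician may exclude participants at excessive risk. No score trigger and no referral role is given.
- Section 19.0: procedure manuals exist but are not among the documents. A manual that allowed referral on a score would contradict section 6.0.
- SAP: nothing on either scale.

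The bar on referral is therefore explicit and the link to adverse-event handling is absent.

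**Step 3: how many results are involved.** Section 12.0 states: "The total number of subjects to be accrued locally is 20". The other 20 of the 40 had completed data collection at the previous institution. For those still to come:

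- session 5: 20 x 1 = 20 results per scale
- F1 to F3: 20 x 3 = 60 results per scale
- all post-baseline: 20 + 60 = 80 results per scale

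These are upper limits. They assume that all 20 are enrolled after the change and that no assessment is missed.

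**Step 4: does the rule, or changing it, touch the main analyses?** The SAP's two tests are on MOBID-2 and fNIRS at Day 5. The first post-baseline NPI and CMAI also fall at session 5, when all five stimulations are done. A referral prompted by a worsening from baseline would come too late to alter treatment or, in practice, those measurements. Alpha, power and the primary analysis are unaffected.

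**The case against.** The strongest reply is that this is a deliberate and defensible choice. The scales are research measures for an exploratory aim, and the sentence limits referral on a score only. It does not limit action on observed behaviour, a caregiver's report or an adverse event. Section 18.0 covers adverse events of any kind, and no other outcome score, MOBID-2 included, is tied to that route. The same caregiver serves throughout (section 6.0) and sees the participant at least 10 hours a week (section 10.0), so marked worsening would probably be noticed anyway. Exposure is five 20-minute sessions with a device described in section 5.0 as non-significant risk. The Background passage on behavioural disorders is about drugs and says nothing about tDCS.

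Most of this stands, and it is why the priority is low. It does not remove the point: the protocol gives no reason for an absolute bar, and MOBID-2 and NRS carry no comparable prohibition.

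A reader might go further in three ways, none of which the documents support.

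- *That the sentence closes the adverse-event route.* It bars referral based on the result; it does not bar adverse-event assessment or notice to the committee.
- *That harm is being missed at some rate.* The documents give no rate of behavioural worsening and no sign that delayed worsening is expected. Any assumed proportion of flagged scores would describe the workload of a proposed rule, not the size of a harm.
- *That a numeric cutoff and a statement that the principal investigator is blinded are needed.* The documents offer no basis for a cutoff on either scale. They call the trial "experimenter- and participant-blinded, randomized, sham-controlled, parallel group" without saying separately whether the principal investigator is blinded, so a review rule should not assert it.

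**Conclusion.** The point holds in a modest form. Section 6.0 forbids clinical referral on an NPI or CMAI result without exception, and no visible text links a marked worsening to adverse-event assessment. The gap matters most at F1 to F3, at most 60 results per scale in the remaining participants, where no side-effects questionnaire is scheduled.

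It is a cheap improvement to participant safety and not a flaw in the trial's inference. Confidence is medium, for two reasons. The procedure manuals and consent form are not in the material and may say more. The protocol also does not say how soon after each assessment the principal investigator reviews the scores; the benefit assumes that this happens while referral is still useful.

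**What to change.** Replace the sentence in Protocol section 6.0 with:

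*The PI will review NPI and CMAI; scores will not routinely trigger referral, but a worsening from baseline that the PI judges clinically marked will be assessed as a possible adverse event under section 18.0 and may lead to clinical referral.*

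This keeps the intent that a research score does not by itself send a participant for review, removes the absolute bar, and names the route. The trigger is clinical judgement, with no numeric cutoff.

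The cost is one sentence in an amendment, with no new data collection. There are three downsides:

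- Some natural fluctuation of dementia symptoms will be assessed as possible adverse events.
- Adverse-event capture will differ slightly between the 20 participants already completed and those enrolled later, which should be noted when safety is reported.
- A referral could influence later secondary measures at F1 to F3.

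None of these outweighs the gain.

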Thermal stimulation. The primary potential risk of thermal stimulation involves burning of the skin; however, we will be using the Medoc TSA-II Neurosensory Analyzer to create thermal stimulation. The TSA-II is covered under FDA 510K #K922052, which mandated both hardware and software safety limits that prevent burning of the skin. The following precautions will be employed in the proposed study: 1) participants will be informed that they can withdraw their arm from the stimulator at any time; 2) the experimenter will continuously monitor stimulus temperature and can manually discontinue stimulation at any point; and 3) the stimulator has a built-in shut-down system to prevent the delivery of prolonged or high-intensity stimuli. Inconvenience to participants will be minimized by delivering brief stimuli that are below the individual's thermal pain tolerance level. These procedures will ensure maximum patient safety and comfort while allowing successful and reliable imaging of the brain.

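### Side effects are asked about only at the end of sessions 1 to 5, so there is no baseline rating and no structured question after treatment ends

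*Protocol*

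**What the plan says.** Protocol section 6.0 says of the assessment that "we will evaluate the presence and severity of possible side effects of treatment at the end of each session", on a 0 to 10 scale. An open question comes first, followed by ten prompted symptoms. Four are tingling, itching, burning and pain at the stimulation site. The other six are "fatigue, nervousness, headache, difficulty concentrating, mood change, and changes in vision or visual perception". For anything reported, "the degree of relatedness to the intervention will be assessed on a 5-point scale".

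The Table 1 row "Side effects questionnaire: secondary outcome" has marks at sessions 1 to 5 and blanks at Baseline, F1, F2 and F3. Text and table agree.

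Other measures run longer. MOBID-2 and the pain NRS are marked at all nine points. The row "BPSD (CMAI, NPI): secondary outcome" is marked at Baseline, session 5 and F1 to F3. The baseline medical history questionnaire covers, among other things, "comorbid conditions, and current medications".

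Section 4.0 describes the study as "including monthly follow-up telephone assessments for 3 months after the completion of intervention", whereas the note under Table 1 describes the same calls as weekly.

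Section 18.0 provides for weekly staff meetings and monthly team meetings, at which possible adverse events are to be identified, and for a Safety Monitoring Committee that adjudicates events. The documents give no adverse-event reporting window and no instruction to ask about harms at the calls. The SAP describes no analysis of side effects.

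**The concern.** Side effects are a listed secondary outcome, and the documents name feasibility and acceptability as specific aim 3. A pilot of this kind will be read for how well the treatment was tolerated, so absolute rates matter as well as the difference between arms.

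The schedule leaves two gaps. First, structured questioning about harm stops at the end of session 5, while pain and behaviour are followed through three further calls. A headache or visual change that starts or continues after the last session is recorded only if someone volunteers it. Participants have cognitive impairment, and section 10.0 requires the caregiver to see them for only 10 hours a week.

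Second, six of the ten prompted symptoms are non-specific and could be present before any stimulation in older people with dementia and chronic pain. With no pre-treatment rating on the same items, within-person change cannot be calculated. The relatedness rating also has to be made without it, and the documents do not say who makes that rating.

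**Working it through.** The plan states no figure on this point, so the check sets the schedule against the other routes by which harm could be recorded, and then sizes the gap.

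**1. Schedule count (Table 1).**
- Time points: Baseline + 5 sessions + 3 calls = 9.
- With the questionnaire: 5. Without it: 9 − 5 = 4 (Baseline, F1, F2, F3).
- Over 40 participants: 5 × 40 = 200 planned administrations, against 9 × 40 = 360 if all points were used.

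**2. Other routes for late effects.**
- Repetition at sessions 2 to 5: effects of sessions 1 to 4 that persist or start later can be reported at the next session, since no recall limit is stated. Nothing comparable follows session 5.
- MOBID-2, NRS, NPI and CMAI at F1 to F3: these could show worse pain, mood or behaviour. They are not a check for headache, fatigue or visual change, and section 6.0 says the NPI and CMAI results will not lead to clinical referral.
- Staff meetings and the Safety Monitoring Committee (section 18.0): these handle events that reach them. They do not ask participants anything.

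**3. Length of the uncovered period.** Three calls at weekly intervals span about 3 weeks; at monthly intervals, about 3 months. The documents support both readings.

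**4. What a missing baseline does to the rates.** This is an illustration with assumed inputs. Let b be the share who would report a symptom regardless of treatment, equal in both arms. Let d = 0.15 be the chance that active treatment produces a report in someone who would not otherwise make one. Then sham = b, active = b + (1 − b)d, and difference = (1 − b)d.

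| b (assumed) | Sham | Active | Difference |
|---|---|---|---|
| 0.10 | 0.100 | 0.235 | 0.135 |
| 0.20 | 0.200 | 0.320 | 0.120 |
| 0.30 | 0.300 | 0.405 | 0.105 |
| 0.50 | 0.500 | 0.575 | 0.075 |

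Background reporting raises both arms and shrinks the difference. It does not create a spurious difference against active treatment. The documents give no value for b or d, so only the direction should be relied on.

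**5. What a change could still deliver.** Section 12.0 says that data collection was complete for 20 participants at the previous institution and that 20 remain to be accrued.
- Active participants among the remaining 20, assuming balanced 1:1 allocation: 20 / 2 = 10.
- One-sided 95% upper bound for 0 events in n: 1 − 0.05^(1/n).
- n = 10: 1 − 0.05^(1/10) = 0.259, or 25.9%.
- Extra administrations: 4 × 20 = 80.

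Under the present schedule, structured data after session 5 give no bound, because the question is not put.

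**The case against.** The best defence is that this is a five-session pilot of a device that section 5.0 describes as non-significant risk, with discomfort that section 20.0 calls transient, using an approach that section 6.0 says is common in other studies. The form is repeated on five occasions with an open question, each report is rated for relatedness, and a randomized, blinded sham arm is the proper control for background symptoms. Meetings and an independent committee stand behind it. Half of the participants have already finished, so an amendment creates two collection schedules in one trial.

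Much of this stands, and it rules out several stronger readings:

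- A reader might infer that delayed or persisting harm cannot be seen at all. The documents do not support this: sessions 2 to 5 can pick up carry-over, and indirect or passive routes exist afterwards. What is missing is systematic questioning after session 5.
- A reader might infer that pre-existing symptoms are counted as side effects. No passage says so. Participants are asked about effects of treatment and relatedness is rated, so misclassification is a risk, not a planned rule.
- A reader might infer that the arm comparison is biased toward harm. The sham arm prevents that; the expected effect is dilution.
- A reader might add heat testing, because section 15.0 says "The primary potential risk of thermal stimulation involves burning of the skin". That concerns an assessment procedure, not the treatment, and it has its own safeguards: monitoring, manual and automatic shut-off, and a temperature cutoff. It is a separate matter and is not part of this point.

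The defence does not supply a baseline rating or any structured question after session 5. A sham arm does not correct the absolute rates within each arm.

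**Conclusion.** The point holds as a gap in scheduling. A listed secondary outcome has no baseline value and no structured collection after session 5, at contacts where other outcomes are already taken. Late effects may be missed over about 3 weeks or about 3 months, depending on which follow-up interval applies. Rates per arm may be inflated by background symptoms and the contrast diluted, by an amount the documents do not allow to be estimated.

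The primary analysis of MOBID-2 is unaffected. The change is worth making because it is cheap, but it would now yield limited information: a 25.9% upper bound if none of about 10 active participants reports a late effect. That rests on balanced allocation among the remaining 20 and on all of them being covered; if some have already started, the bound widens.

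**What to change.** For participants still to be enrolled:

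1. Mark the existing questionnaire in Table 1 at Baseline, before heat testing and stimulation, and at F1, F2 and F3.
2. At sessions 2 to 5, ask also about symptoms since the previous session.
3. Add to the SAP that side effects will be reported by arm as new or worse than baseline, where a baseline exists.

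For the 20 participants already completed, report the session 1 to 5 data as collected, separately, and state the limitation.

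Reconcile the follow-up interval between section 4.0 and the Table 1 note, since it sets the period that the added questions would cover.

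The cost is a small amendment to Table 1, the form and the SAP, about 80 further administrations of a short form, and slightly longer contacts, with no new visit or staff. More unrelated events will be logged, and the trial will carry two collection schedules that cannot be pooled for the new-or-worse summary.
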